23.3. Analysis of pilot data

At the end of the internal pilot, data will be analysed descriptively to assess whether or not to proceed with the remainder of the trial as is, with modifications or to stop at that point. The DSMC will make a recommendation to the TSC who will inform the Sponsor and Funder.

23.4. Statistical Plan and Analysis

All analyses will be performed in Stata version 17.0 (89) or later. A detailed statistical analysis plan (SAP) will be written up prior to data analysis.

Summary of baseline data and flow of patients

Participant flow will be depicted according to the CONSORT 2010 Statement. (90) Baseline data will be summarised by trial group, normally distributed variables described by their means/standard deviations, skewed continuous variables by their medians/interquartile ranges and categorical variables by their frequencies/percentages. Scoring rules for the study instruments will be detailed in the full statistical analysis plan.

Primary outcome analysis

The primary outcome will be analysed, following intention-to-treat principles, using a linear mixed effects model with fixed effects for time point (2 dummy variables), gender, continuous Child Pugh score, randomisation group, randomisation group by time point interaction and adjusting for SFLDQoL score at baseline, and with a random effect for participant to handle the correlation between repeated measurements. The model will be fitted using restricted maximum likelihood estimation. We will report the estimated treatment differences between LTAD and LVP groups at weeks 4, 8 and 12, their 95% confidence intervals and p values.

Secondary outcome analysis

Secondary outcomes will be analysed using mixed effects regression models appropriate to outcome type, adjusting for baseline measure of outcome, in addition to the fixed and random effects as detailed for the primary outcome analysis.

Subgroup analyses

Analysis will be stratified to include, but not limited to, liver prognostic scores, survival, development of peritonitis, ascitic fluid albumin level and presence of informal caregivers.

Participant population

All data collected on all randomised participants will be analysed in the arm to which they were randomised.

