9.4. Primary endpoint/outcome

The primary outcome is liver specific HRQoL assessed at 3 months using the SFLDQoL questionnaire (34), the only HRQoL tool validated in advanced cirrhosis.

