23. STATISTICS AND DATA ANALYSIS

23.1. Sample size calculation

Following on from the HTA Committee and PPI feedback and the International LIverHope Consortium's recommendations (73), we have selected HRQoL as our primary outcome.

The minimal clinically important difference (MCID) is the mean change in HRQoL scores for patients reporting a minimal yet perceptible change in health between the baseline and follow-up assessments. (85) In the ongoing LiverPal Study (one of the largest palliative trial in the United States (86), an MCID of 9 points on the FACT-Hep questionnaire was used; and in a study assessing LTADs in cirrhosis (87), an MCID of 10 points was chosen (SF-36 questionnaire). While these studies show the use of the MCID to inform sample size in palliative trials, neither of the tools selected are validated in advanced cirrhosis. As we will be using the SFLDQoL, a sensitive and validated questionnaire in advanced cirrhosis (34), we have selected a MCID of 8 points.

In our feasibility REDUCe study (46), the pooled baseline mean across SFLDQoL domains (excluding sex function) was 56.4 (SD=26.1). With 93 participants in each group for the analysis, we will have 90% power for 5% significance to detect an adjusted difference in mean SFLDQoL scores of 8 points between the LTAD and LVP groups at the end of 3-months (effect size 0.31). This effect size falls within Cohen's recommended cut offs for small (0.20) to moderate (0.50) effect size. (88) We will assume a correlation between baseline and the 3 follow-up measurements of 0.48 which is the lower bound of the 95% Confidence Interval for the correlation (point estimate 0.77) (from REDUCe study data). (46) With an expected 40% attrition (REDUCe study) (46), we will recruit 310 participants in total for the trial.

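### The primary model assumes one variance and one correlation across weeks 4, 8 and 12, so its week-12 standard error is miscalibrated if that fails; relaxing the assumption costs almost nothing

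*Protocol*

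**What the plan says.** The primary endpoint is fixed at one time point: "The primary outcome is liver specific HRQoL assessed at 3 months using the SFLDQoL questionnaire" (section 9.4). Section 23.4 then writes the model out. The fixed effects are time point (two dummies), gender, continuous Child Pugh score and group, followed by "randomisation group by time point interaction and adjusting for SFLDQoL score at baseline". Dependence within a participant is handled "with a random effect for participant to handle the correlation between repeated measurements". On estimation, "The model will be fitted using restricted maximum likelihood estimation". On output, "We will report the estimated treatment differences between LTAD and LVP groups at weeks 4, 8 and 12", with confidence intervals and p values.

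Only group is interacted with time, so the three visits share one baseline slope. The section names no unstructured covariance, visit-specific residual variance, random slope or robust standard error.

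The sample size in section 23.1 makes a matching simplification: "We will assume a correlation between baseline and the 3 follow-up measurements of 0.48". It describes 0.48 as the lower 95% confidence limit of a correlation whose point estimate is 0.77.

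**The concern.** A single participant random effect with independent residuals gives every follow-up visit the same variance, and every pair of visits the same correlation, once baseline is adjusted for. The model therefore attaches a variance pooled over weeks 4, 8 and 12 to the week-12 contrast.

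Section 8 puts average life expectancy with refractory ascites at 6-12 months. In such a population the baseline score may well predict week 12 less closely than week 4. If so, the residual variance at week 12 exceeds the pooled value, even with a constant raw SD, and the week-12 interval is too narrow. Attrition adds to this: a model that overstates the link between distant visits borrows too much from weeks 4 and 8 for the 40% expected to have no week-12 score. At stake is the calibration of the p value and interval on which the trial's conclusion rests.

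**Working it through.** **Inputs from the protocol.** 310 randomised 1:1, so 155 per arm; 40% attrition, so 155 × 0.60 = 93 per arm at week 12; SD 26.1; target difference 8 points; 90% power; 5% significance, taken as two-sided; correlation 0.48.

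**Assumed, because the protocol does not give them.** The correlation at each lag; the SD at each follow-up; retention of 87%, 73% and 60% at weeks 4, 8 and 12; dropout completely at random.

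**The plan's own figure.** ANCOVA on the mean of three exchangeable follow-ups has variance factor f = (1 + 2r)/3 − r². With r = 0.48, f = 0.6533 − 0.2304 = 0.4229. Then n = 2(1.960 + 1.282)² f / d². With d = 0.31 this is 2 × 10.51 × 0.4229 / 0.0961 = 92.5, so 93 per group; unrounded d = 8/26.1 gives 95. Then 186/0.60 = 310. The stated 93 and 310 reproduce, and they do so under exchangeability.

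**Mechanism with complete data and constant SD.** Let r_t be the correlation of baseline with visit t. The common slope settles at b = mean of the r_t. The residual variance at visit t, in units of SD², is v_t = 1 − 2b·r_t + b². The model uses the mean of the v_t; the week-12 contrast actually has v_12. So the SE ratio (reported/true) is √(mean v / v_12), and type I error is 2Φ(−1.96 × ratio).

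- Exchangeable: all v_t are equal, ratio 1.00, type I error 5.0%.
- Mild decay, r = 0.70, 0.60, 0.50: b = 0.60; v = 0.52, 0.64, 0.76; mean 0.64; ratio √(0.64/0.76) = 0.918; type I error 7.2%.
- Steep decay, 0.77 per lag, r = 0.770, 0.593, 0.457: b = 0.607; v = 0.434, 0.649, 0.814; mean 0.632; ratio 0.881; type I error 8.4%.

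**With 40% attrition.** The stated model was fitted in large samples to each pattern, and its reported week-12 SE was compared with the true (sandwich) SE. Correlations are at lags of 4, 8 and 12 weeks; SD changes are linear to week 12.

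| Assumed pattern | Reported SE | True SE | Type I error |
|---|---|---|---|
| Exchangeable, 0.48 or 0.77 | equal to true | – | 5.0% |
| 0.60/0.55/0.50 | 3.08 | 3.22 | 6.1% |
| 0.80/0.77/0.74 | 2.31 | 2.47 | 6.6% |
| 0.70/0.60/0.50 | 2.89 | 3.22 | 7.9% |
| 0.77 per lag | 2.81 | 3.33 | 9.8% |
| 0.77 per lag, SD +20% | 3.18 | 3.95 | 11.5% |
| Constant 0.48, SD +20% | 3.70 | 3.95 | 6.6% |
| Constant 0.48, SD −20% | 2.89 | 2.64 | 3.2% |
| 0.77 per lag, SD −20% | 2.46 | 2.73 | 7.7% |

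**Simulation.** In 3,000 simulated trials per pattern, fitted by REML, type I error was 4.7% (exchangeable 0.48), 9.5% (0.77 per lag) and 10.9% (0.77 per lag, SD +20%). A set of 1,000 per pattern with retention 85/72/60% gave 10.9% and 12.3% for the last two.

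**Where the narrowing comes from.** If correlation decays only among the follow-ups (0.77 to 0.48, baseline correlation held at 0.48), complete data show no narrowing and 40% attrition gives 5.9%. If only the baseline correlation falls (0.77/0.62/0.48, follow-ups correlated at 0.6 throughout), type I error is 9.1%. The falling baseline-to-follow-up correlation does most of the damage.

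**Effect of the remedy.** Under 0.77 per lag with attrition, an unstructured covariance with visit-specific baseline slopes has a correctly calibrated SE of 3.21. That is also smaller than the stated model's true SE of 3.33. Visit-specific slopes alone would not be enough: with complete data the residual variances become 1 − r_t² = 0.407, 0.648, 0.792, mean 0.616, and √(0.616/0.792) = 0.882, practically unchanged.

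**The case against.** **The protocol's correlations do not show decay.** A reader might infer from 0.77 and 0.48 in section 23.1 that correlation falls over time, since 0.77 cubed is 0.46. The section does not support this: the two figures are the point estimate and lower confidence limit of one correlation. This objection stands in full. The steep pattern is an assumption with no anchor in the document, and milder decay gives only about 6-8%.

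**The direction is not fixed.** A reader might infer that the interval must be too narrow. It need not be. The scale is bounded at 0-100 (section 17.2) and only participants still under follow-up are scored at week 12, so the SD could fall. At constant correlation, a 20% fall makes the interval too wide. This also stands, although steep decay stays anti-conservative even then (7.7%).

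**Residual structure belongs in the SAP.** Section 23.4 promises a detailed SAP, and visit-specific residual variances or robust errors could be added without contradicting the protocol. This stands in part: equal variance and correlation follow from the model as written only with default independent residuals. But the section is not silent. It lists the fixed effects, gives one baseline term and names the device meant to carry the correlation, so the specification is a stated choice open to comment.

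**A random intercept with baseline adjustment is standard.** True, and it is valid under exchangeability. The protocol offers no evidence that exchangeability holds here.

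**Conclusion.** The point holds as a conditional one. As written, and with ordinary independent residuals, the primary model is calibrated at week 12 only if variance and correlation are equal across visits given baseline. The protocol neither states nor supports that condition.

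Across the patterns examined, the nominal 5% type I error runs from about 3% (SD shrinking 20%, constant correlation) through 5.0% (exchangeable) and 6-8% (mild decay) to about 10% (steep decay) and 11-12% (steep decay with SD growing 20%). These figures rest on SD 26.1 at baseline, 155 per arm, the assumed retention and dropout completely at random; informative dropout is a separate problem. The documents do not support a claim that the trial's type I error will be doubled, because that needs the steep pattern. This is a cheap improvement to make before the SAP is agreed, not a proven fault in the primary result.

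**What to change.** In section 23.4, or in the SAP with the change recorded:

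- Replace the participant random intercept with an unstructured residual covariance over weeks 4, 8 and 12, fitted by REML with Kenward-Roger degrees of freedom. This restores calibration.
- Add a baseline SFLDQoL by time-point interaction, so that each visit has its own baseline slope. This recovers precision when baseline predicts later visits less well.
- Name a fallback in advance, such as a heterogeneous autoregressive structure, in case the unstructured model does not converge.

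The cost is four more covariance parameters (six instead of two) and two more fixed effects, with about 186 participants expected at week 12. If the visits are exchangeable after all, essentially nothing is lost. The sample size need not change on account of this point.

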8.3. Long-term abdominal drain use in cirrhosis

There have been national calls to improve palliative care in advanced cirrhosis. (42) However, LTADs are not routinely used in cirrhosis as firstly, those with cirrhosis can have a complex symptom burden and psychosocial issues like addiction, making community care potentially challenging. Secondly, unlike those with cancer, patients with cirrhosis are at higher risk of ascitic fluid infection (peritonitis) due to increased bacterial translocation, gut dysbiosis and immune dysfunction. (9) The concern is whether LTADs could further increase this infection risk. These issues were highlighted in our national survey of Gastroenterologists. (43)

A systematic review assessed LTADs in refractory ascites due to advanced cirrhosis (18 studies, all rated to be of poor quality, 176 patients). (44) Insertion success was 100% with no further ascites-related hospitalisations in 14/18 studies where data were provided. Peritonitis rates (12.7%) were more than two fold higher than that reported in malignant ascites (5.9%) (38) Recent data comes from the REDUCe Study (45-46), comparing palliative LTADs vs. LVP in patients with refractory ascites due to advanced cirrhosis. This randomised controlled trial (RCT) was designed to determine feasibility, assessment tools, preliminary cost effectiveness and outcome measures for the main trial. Of the 59 eligible patients, 36 (61%) were randomised with 21 (58%) completing the 3-month study. Both groups received prophylactic antibiotics for the study duration. LTAD insertion was successful in all participants, only 2/15 (13%) requiring further hospitalisation specifically for ascites. Peritonitis incidence (LTAD vs. LVP) was 6% vs.11%, self-limiting cellulitis (none requiring hospitalisation) being 41% vs. 11% respectively. The LTAD group spent less ascites-related study time in hospital, the average fortnightly total costs being about 15% lower. Symptom and HRQoL scores, the latter

REDUCe 2 protocol v2 20.06.22

assessed using SFLDQoL questionnaire (34), were highly variable in both groups, likely reflecting the small sample size. (46) A small qualitative sub study indicated LTAD acceptability by patients and nurses. (47) We achieved our study success criteria: attrition 42% (pre specified not >50%); LTAD complications requiring removal 0% (pre specified <10%); uptake/completion of questionnaires/interviews: \geq 80% (pre specified 80%).

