9.5. Secondary endpoints/outcomes

- Cumulative peritonitis incidence in the LTAD and LVP groups
- Symptoms in LVP and LTAD groups assessed using the Ascites Q (74)
- Informal caregiver impact in LTAD and LVP groups assessed using the CRRS (75)

- Health resource utilisation in LTAD and LVP groups (modified AHCR (76-77) for community service use; hospital records for hospital service use using an inhouse designed questionnaire)
- Generic HRQoL and cost-utility analysis based on QALYs using EQ-5D-5L (78-79)
- Patient, caregiver and health care professional perceptions/perspectives of LTAD and LVP using qualitative methods

Table 2. Table of Endpoints / Outcomes

Objectives	Outcome measure	Timepoint(s) of evaluation of this outcome measure (if applicable)
Primary		
To assess whether palliative LTADs result in better health related quality of life (HRQoL) compared to LVP in patients with refractory ascites due to advanced cirrhosis. Secondary	Liver specific HRQoL assessed at 3 months with the SFLDQoL questionnaire	To be assessed at baseline and four weekly
To assess impact of LTADs and LVP on:		
Infections (especially peritonitis)	Cumulative peritonitis incidence in the LTAD and LVP groups	To be assessed at 3 months
Symptoms	Symptoms in LVP and LTAD groups assessed using Ascites Q	To be assessed at baseline and fortnightly for 3 months
Caregiver workload	Informal caregiver impact in LTAD and LVP groups assessed using CRRS	To be assessed at baseline and four weekly for 3 months

Health resource utilization	Health resource utilisation in LTAD and LVP groups: community service use (modified AHCR) and hospital records for hospital service use (inhouse designed questionnaire)	To be assessed at baseline and fortnightly, hospital service use at 3 months
	Generic HRQoL and cost-utility analysis based on QALYs using EQ-5D-5L	To be assessed at baseline and fortnightly
Explore perceptions of LTADs and LVP by patients, informal caregivers and healthcare professionals with qualitative interviews.	Patient, caregiver and health care professional perceptions/perspectives of LTAD and LVP using qualitative methods	Interviews (optional) to be conducted throughout the trial

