12.2. Exclusion criteria

- Loculated and or chylous ascites
- Evidence of active infection that in the investigator's opinion would preclude insertion of LTAD (for example, bacterial peritonitis) such patients would need to receive appropriate treatment and could then be reconsidered
- A candidate for liver transplantation and or TIPS
- Psychosocial issues which in the opinion of the medical team will preclude study participation
- Pregnancy all women of childbearing age must have a negative pregnancy test
- Lacks capacity to give informed consent

Participants whose first language is not English can have materials translated so as not to exclude their participation. Participants will not be excluded if they are already participating in another ongoing study, as long as their researchers are confident that participation in the current study will be logistically feasible and not too onerous for the participants. Approval for co-enrolment may be needed by on-going study Chief Investigator. Patients will also not be excluded from participation in the study in relation to their place of care/residence, for e.g. if they are in or move to a hospice/ care home. Study recruitment would remain unchanged with patient identification and consent undertaken in the hospital sites and follow-up data collection in usual place of residence (including care homes).

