Concomitant medication review	X	X	X	X	X	X	Х
Ascites questionnaire (Ascites Q) completion (patient)	X	X	X	X	X	X	X
Liver specific HRQoL (SFLDQoL) questionnaire completion (patient)	X		X		Х		X
Generic HRQoL (EQ5D-5L) questionnaire completion (patient)	X	X	X	X	X	X	X
Care giver questionnaire (CRRS) completion (caregiver)	X		X		X		×

Community service use (modified AHCR) questionnaire completion (patient)		X	X	X	Х	Х	Х	Х
Hospital service use in house designed questionnaire completion (research team member)								X
Optional qualitative interviews (patients, informal caregivers and healthcare professionals) will be conducted throughout the study. Only one interview per participant			X	X	X	X	X	X

¹ PT and or INR and platelet count and diagnostic ascitic tap need to be checked within 7 +/-3 days of LTAD insertion; Spontaneous bacterial peritonitis defined as ascitic white cell count > 500 cells/mm³, and or neutrophil count > 250 cells/mm³ and or a positive ascitic fluid culture. (64)

² To be done in LVP group at each drainage as is current standard of care, and LTAD patients only if suspicion for peritonitis. In those with LTAD and clinical suspicion for peritonitis, take ascitic fluid sample for analysis from both from LTAD and via a separate ascitic tap

³ For LTAD only: Prior to LTAD insertion correct INR and platelet count as per local trust guidelines. If no local guidelines available use the following: if INR≥1.5 and platelet count ≤ $50x10^9$ 2 units of Fresh Frozen plasma and 1 -2 pools of platelets to be transfused prior to LTAD insertion

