Routine ascitic fluid analysis in the LVP group will be performed at each drainage as is currently standard of care. In the LTAD group, routine ascitic fluid analysis will not be performed due to the likelihood of growing skin contaminants (80), the clinical significance of which remains uncertain. In those with a LTAD, ascitic fluid analysis will **ONLY** be performed if there is clinical suspicion for peritonitis: fever, abdominal pain, increased white cell count, worsening hepatic decompensation or renal function. In such instances the ascitic fluid sample will be taken for analysis from both the LTAD as well as via a separate ascitic tap. Peritionitis will be diagnosed if ascitic fluid neutrophil count is > 250/mm³, and or ascitic fluid white cell count is >500/mm³ and or if ascitic fluid culture is positive. (9, 64) Peritonitis will be treated as per current guidelines. (9, 64) Development of peritonitis will not necessarily mandate LTAD removal. This needs to be decided on a **case-by-case basis** after discussion between site teams and the CI.

LTAD (Group 1) post drain insertion care (also see Figure 1)

- The research team will explain to the patient and informal caregivers how the LTAD will be used and provide them with the drainage kit, which will include at least two weeks supply of drainage bags. The Research teams will provide patients with the LTAD manufacturer information sheet and discharge letter, the latter also being sent to the GP and community nursing team. The discharge letter will state that patients have been discharged with a LTAD. LTAD manufacturer details are included in the discharge letter. An additional community nurse referral will be sent to the community teams with basic instructions on LTAD management.
- The research team will also contact the appropriate lead community nurse to update them. This will ensure that home visits can be organised by the community team to

perform recurrent drainage and arrange necessary disposal of clinical waste. The research team will also inform the LTAD manufacturer so that they can organise additional bespoke training and support for participants/informal caregivers if needed and ensure supply of drainage bags

• The patient and community teams will be provided with the contact number for the research team. The patients will also be provided with written information describing LTAD management should they be admitted to hospital out of hours so that clinical teams are aware.

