23.5. Procedure(s) to account for missing or spurious data

In accordance with MORECare guidance on palliative trials (66), we will summarise attrition in each group as due to mortality, illness and withdrawal. We will assume missing quantitative data to be missing not at random (MNAR) unless there is evidence to the contrary and test results using a range of plausible values. (91-94) If we find evidence of differential attrition, we will, in sensitivity analyses, explore MNAR scenarios by first multiply imputing missing outcomes and then add/subtract (as appropriate) constants from the scores in the most impacted arm and re-estimate the treatment effect. In a systematic review and meta-analysis of 108 palliative trials, there was no evidence of differential attrition related to mortality (95) and we would expect the same in our trial.

Whilst attrition in the feasibility trial (46) was greater in the LTAD arm than in the LVP arm, estimates were imprecise due to the small sample size. The estimated difference in attrition proportions between the two arms was 10.3%, 95% CI (-21.8%, 42.4%). Potential reasons for differential attrition include the contrasting nature of the interventions - participants may prefer to be allocated to LTAD over LVP. Differential attrition may also be due to potential LTAD/LVP related complications. However, our PPI group have stated that the disappointment of being randomised to LVP would be mitigated by the fact that all participants would receive close follow up and fortnightly home visits. Also, irrespective of which arm they were randomised to, participants could take altruistic pride in the fact that they were contributing to the improvement of palliative care for future generations. We will aim to avoid differential attrition. However, if we find evidence of differential attrition, we will, in sensitivity analyses, explore MNAR scenarios e.g. by first multiply imputing missing outcomes and then add/subtract (as appropriate) constants from the scores in the most impacted arm and re-estimate the treatment effect.

23.6. Other Statistical Considerations.

A full statistical analysis plan will be agreed prior to final analysis. Any deviation from this plan will be fully documented in the final trial report.

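### Survival and development of peritonitis are listed as subgroup variables, but both arise after randomisation, so LTAD–LVP differences within those strata are not randomised comparisons

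*Protocol*

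**What the plan says.** Under the subgroup heading in Protocol section 23.4, the plan states that analysis will be stratified by an open-ended list of variables: "liver prognostic scores, survival, development of peritonitis, ascitic fluid albumin level and presence of informal caregivers". No outcome, model or test is named. Neither section 23.4 nor section 23.5 limits survival or peritonitis to descriptive use, a landmark analysis or a pre-randomisation version of the variable.

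Other sections show what these two variables are:

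- **Peritonitis as an outcome.** Section 9.5 lists "Cumulative peritonitis incidence in the LTAD and LVP groups" as a secondary endpoint, and Table 2 assesses it at 3 months. Section 12.2 excludes patients with active infection such as bacterial peritonitis until it has been treated, so its development is a follow-up event.
- **Peritonitis detection.** Section 16.1: "Routine ascitic fluid analysis in the LVP group will be performed at each drainage as is currently standard of care". Footnote 2 to Table 3 has the tap done in "LTAD patients only if suspicion for peritonitis".
- **Survival.** Section 23.5 treats death as a source of missing data: "we will summarise attrition in each group as due to mortality, illness and withdrawal".

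**The concern.** A subgroup effect has a causal reading because, within levels of a variable fixed before allocation, the arms are still randomised. Once the stratum is defined by something that happens afterwards, that no longer holds if the arm affects the event, the kind of patient who has it, or how it is detected. LTAD patients recorded with peritonitis, or LTAD survivors, are then not exchangeable with their LVP counterparts.

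The protocol itself gives reason to expect such links. Section 8.3 raises the worry that LTADs could increase infection and reports peritonitis in 6% (LTAD) vs 11% (LVP) in the feasibility trial. Sections 13.1 and 16.1 fix different detection rules by arm. Section 8.1 says that poorer quality of life predicts mortality, so the outcome is related to one of the proposed strata.

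At stake is the interpretation of secondary results on infection and death. A difference among survivors or among peritonitis cases, reported as a prespecified subgroup effect, would carry more authority than it deserves.

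**Working it through.** **1. The plan's own numbers.** Section 23.1 gives 93 analysed per group, SD 26.1, difference 8 (effect size 0.31), correlation 0.48, 90% power, 5% significance (two-sided assumed) and 40% attrition. For the mean of three follow-ups adjusted for one baseline, the variance factor is (1 + 2×0.48)/3 − 0.48² = 0.423. Then n = 2 × (3.242/0.31)² × 0.423 = 92.5, so 93 per group. With the unrounded 8/26.1, n is 94.6, which is close. 93/(1 − 0.40) = 155 per arm, or 310 in total. The planned size is reproduced, and 155 per arm is used below.

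**2. Size of the peritonitis stratum.** At the feasibility rates, 155 × 0.06 = 9.3 and 155 × 0.11 = 17.05, so about 9 vs 17. If only the 93 per arm expected to be retained are counted, and attrition is unrelated to peritonitis, 93 × 0.06 = 5.6 and 93 × 0.11 = 10.2, so about 6 vs 10. With 9 vs 17, the unadjusted standard error is 26.1 × √(1/9 + 1/17) = 10.8 points, and the 95% half-width is about 21 points.

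**3. Bias from unequal detection, with equal infection risk and no LTAD effect.** Assumptions not in the protocol: symptomatic cases score 15 points lower, silent cases score no lower, a proportion s of cases is symptomatic, and 70% of silent cases are found under LVP but none under LTAD. All recorded LTAD cases are then symptomatic. Among recorded LVP cases the symptomatic share is s/(s + 0.7(1 − s)).

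- s = 0.5: share 0.5/0.85 = 0.588; false difference −15 + 15 × 0.588 = −6.2 points.
- s = 0.8: share 0.8/0.94 = 0.851; false difference −15 + 15 × 0.851 = −2.2 points.

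**4. Bias from unequal event rates, with no LTAD effect.** Let quality of life and a latent risk of the event have correlation −ρ, with ρ of 0.3, 0.5 or 0.7 (assumed). With event risk p and normal density φ at its cut-off, the mean score shifts by −ρ × 26.1 × φ/p in those with the event and by +ρ × 26.1 × φ/(1 − p) in those without. For 6% vs 11%, φ/p is 1.985 vs 1.709, so the false difference among cases is −ρ × 26.1 × 0.276: −2.2, −3.6 and −5.0 points. Simulation of the same model (155 per arm, unadjusted, scores available for everyone) gave:

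| Event rates, LTAD vs LVP | Stratum | False difference, ρ = 0.3 to 0.7 | Rejection at nominal 5% |
|---|---|---|---|
| Peritonitis 6% vs 11% (feasibility) | with peritonitis | −2.1 to −5.1 | 5.5% to 9.5% |
| Peritonitis 6% vs 11% | without peritonitis | −0.7 to −1.5 | 5.5% to 8.2% |
| Death 30% vs 40% (assumed) | survivors | −1.2 to −2.7 | 6% to 14% |
| Death 20% vs 40% (assumed) | survivors | −2.3 to −5.4 | 10% to 41% |
| Equal rates, same mechanism | either | about 0 | 5% |

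The last row shows the condition: no bias arises if the arm changes neither the event, nor its mechanism, nor its detection. For peritonitis the detection rule differs by design.

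**5. Survival and the week-12 score.** SFLDQoL is collected at baseline and weeks 4, 8 and 12 (Table 3). Someone who dies before week 12 has no week-12 score but may have scores at weeks 4 and 8, which enter the mixed model of section 23.4. In the non-survivor stratum the week-12 contrast is therefore unobservable, while the earlier contrasts are not.

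**The case against.** The strongest reply concerns weight. These are subgroup analyses: no decision rule, pilot criterion or significance level depends on them, and a detailed SAP is to follow. The simulated biases rest on assumed correlations, death rates and symptom deficits. The feasibility rates come from only 36 randomised patients. A bias of 2 to 6 points in a stratum with a standard error of about 10.8 would seldom produce a significant result. Section 23.5 expects no difference between arms in mortality-related attrition. Part of the remedy is already in place, since peritonitis is a secondary endpoint by arm and deaths are summarised by group.

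All of that stands as a limit on size and severity. It does not remove the point, because the protocol itself names the two variables and nothing in it confines them to description.

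Stronger readings that a reader might infer, and that the protocol does not support:

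- *The non-survivor stratum is empty.* It lacks only week-12 scores; week 4 and week 8 data can exist.
- *A false effect will be reported.* The text names no outcome or test, and the bias can be nil if events, mechanism and detection do not depend on arm.
- *The main result is compromised.* The primary comparison does not use these strata.
- *Deleting survival from the list cures the problem of deaths.* Truncation by death remains in the main week-12 analysis whatever the subgroup list says.

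**Conclusion.** The point holds at moderate weight: it should be fixed, but it does not threaten the primary analysis. As written, section 23.4 presents stratification by two post-randomisation events as subgroup analysis. Reading this as stratification of the LTAD–LVP comparison is an inference, though the natural one under that heading.

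Differences within these strata are not randomised comparisons and can be biased with no true effect. The illustrations give a few points against a target of 8: about 2 to 6 among peritonitis cases and about 1 to 5 among survivors. These figures rest on assumptions outside the protocol; they show what is possible and do not predict a result. For peritonitis, low precision (about 9 vs 17 patients at the feasibility rates) is as much a limitation as bias.

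**What to change.** In section 23.4, and in the SAP:

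1. Delete survival and development of peritonitis from the subgroup list.
2. Restrict subgroups to values measured before randomisation, for example Child-Pugh or MELD score, ascitic fluid albumin and caregiver presence at screening. The timing needs stating, because Table 3 repeats the liver scores at every visit and allows randomisation up to 10 days before the baseline visit.
3. Keep peritonitis as an outcome compared by randomised arm, and add a comparison of death by 3 months by arm.
4. Label any summary of quality of life by death or peritonitis as descriptive and non-causal.

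The cost is a few lines of text, best changed before outcome data by arm are seen. Deleting the two variables needs no new data, and deaths are already recorded. One item to confirm is ascitic fluid albumin: Table 3 names cell counts and culture for the diagnostic tap but not albumin, so that subgroup depends on a pre-randomisation value being captured.
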